5.2. Subgroups of Interest

Analyses of subgroups of subjects may be used to better understand the biological activity of ALPN-101 in subjects with SLE. Subgroup analyses will be performed on a case-by-case basis as post-hoc analyses. Possible subgroups of interest, depending on available data, and may include, but are not limited to:

- Geographic region
- Age group: <50 years, ≥ 50 years
- Race
- Baseline SLEDAI-2K: $<10, \ge 10$
- Baseline corticosteroid use: >7.5 mg/day, <7.5 mg/day
- Sex at birth: Male, Female

• Body Mass Index (BMI): $<30 \text{ kg/m}^2$, $\ge 30 \text{ kg/m}^2$

6. ANALYTIC DEFINITIONS

6.1. Baseline and Change from Baseline

Baseline values are the last values recorded prior to the first administration of study drug, unless otherwise specified.

Change from baseline values for a subject are derived as the subject's post-baseline value minus the subject's baseline value of the same variable.

Percent change from baseline is calculated by dividing the change from baseline value by the baseline value as follows:

Percent change from baseline = ((post-baseline value – baseline value) / baseline value) x 100

6.2. Treatment Exposure Duration

Duration of treatment exposure is calculated as the number of days between the date of a subject's last dose of study drug and the date of the first dose of study drug. Intervals of dosing interruption between a subject's first and last doses will not be deducted from the overall treatment duration. That is:

Date of last dose of study drug – date of first dose of study drug + 1

6.3. Overall Treatment Compliance

Overall treatment compliance (%) with protocol-specified treatment for a subject will be calculated as:

100 x (number of doses received)/(weeks of study participation prior to the end of treatment/2)

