- Significant non-compliance with study procedures to a degree that would put the subject at risk for continued participation in the trial as determined by the Investigator or the Medical Monitor.

• Development of active neuropsychiatric SLE (excluding lupus headache) sufficiently severe to interfere with ability of the subject to provide ongoing informed consent.

• Investigator decision: Investigator believes it is in the best interest of the subject to discontinue treatment with study drug.

Subjects who prematurely discontinue treatment with study drug should have all procedures outlined in the EoT visit, as well as an unscheduled ECG, performed as soon as possible, and not later than the next scheduled visit.

To minimize missing data for efficacy and safety assessments, subjects who prematurely discontinue treatment, and who do not withdraw consent, should otherwise continue with their regular study visit schedule without receiving study drug. In subjects who are unable to continue their regularly scheduled visits, a follow-up phone call should occur approximately 8 weeks (corresponding to 5X half-life) after the last dose of study drug to determine the status of any ongoing AEs/SAEs or the occurrence of any new AEs/SAEs.

Discontinuation from the Study (Early Termination)

In addition to the criteria for discontinuing study drug summarized above, individual subjects may be discontinued from the study prematurely (i.e., prior to Day 197) for any of the following reasons:

- Subject decision / withdrawal of consent; subjects can request to be discontinued from participation in the study at any time for any reason
- Investigator decision: Investigator believes it is in the best interest of the subject to be withdrawn from the study

For subjects who withdraw from the study prematurely (i.e., prior to Day 197), the End of Study (EoS) evaluations should be completed if possible, preferably within 2 weeks of study drug discontinuation. In addition, a follow-up phone call should occur approximately 8 weeks (corresponding to 5X half-life) after the last dose of study drug to determine the status of any ongoing AEs/SAEs or the occurrence of any new AEs/SAEs.

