6.4.12. Day 169 (End of Treatment)

- Record AEs and concomitant medications
 - Photography of any oral mucocutaneous lesions reported as AEIs, if applicable
- Perform problem-oriented physical examination; obtain vital signs and weight
- Using the provided kit, collect blood and urine samples for safety laboratory evaluations and clinical biomarkers of SLE
- Using the provided kit, collect blood samples for PK
- Perform urine pregnancy test for WOCBP using the provided kits
- Complete the SDI

NOTE: Additional procedures and/or documentation to support diagnosis of new damage, compared to Baseline, may be required (e.g., radiographic evidence to support diagnosis of avascular necrosis; photography to support new diagnosis of skin damage; other); refer to Procedures Manual.

• Perform Investigator disease activity assessments: BILAG 2004, SLEDAI-2K 30, PhGA, CLASI,

- Skin photography, if applicable
- Obtain Subject's disease assessments: PtGA, SF-36, FACIT-F (13-item)

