6.6. Unscheduled Visits

6.6.1. Early Termination

If a subject withdraws consent for study participation prior to Day 197, the EoS evaluations should be completed if possible, preferably within 2 weeks of study drug discontinuation. In addition, a follow-up phone call should occur 8 weeks after the last dose of study drug to determine the status of any ongoing AEs/SAEs or the occurrence of any new AEs/SAEs.

As noted in §4.3, subjects who prematurely discontinue treatment with study drug (i.e., due to subject choice, Investigator decision, an AE or other contraindication for ongoing receipt of study drug, etc.), and who do not withdraw consent, should have all procedures outlined in the EoT visit as well as an unscheduled ECG, as soon as possible, preferably within 2 weeks. Afterwards, subjects should resume following the regular visit schedule as outlined in Table 1, and adhere to all study procedures except for study drug dosing. As the subject has discontinued study drug, all concomitant medication restrictions as outlined in §8.2.2 no longer apply. If at any point subsequently a subject no longer wants to provide assessments (withdrawal of consent) following discontinuation of study drug and completion of the EoT assessments, an EoS visit is not required.

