7.2. Preparation and Dosing

Subject eligibility must be independently confirmed prior to randomization and administration of study drug.

The planned dosing regimen for this study is 3 mg/kg ALPN-101 or placebo IV administered Q2W for 12 total doses. If a dose of study drug is missed, consult with the Medical Monitor. Dose or dose intensity may be decreased based on DMC recommendation and Sponsor decision; refer to §4.3.

Doses of study drug are calculated and prepared based on each subject's body weight at Baseline, rounded to the nearest kilogram, unless weight changes by more than 10%; in that case doses of study drug will be calculated and prepared based on the subject's most current body weight. Study drug will be prepared in accordance with instructions in the Pharmacy Binder and will be infused over approximately 30 minutes (±15 minutes) using a volumetric pump with a 0.2 micron in-line filter. Study drug is NOT to be administered as an IV push or bolus injection.

Subjects should be observed for at least 2 hours following their first infusion of study drug and for 30 minutes following each subsequent infusion.

The Investigator is responsible for the education of study staff in the correct administration of study drug.

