4. STUDY DESIGN

4.1. General Description

This is a Phase 2, multicenter, multinational, randomized, double-blind, placebo-controlled, parallel-group study to evaluate the safety, tolerability, efficacy, immunogenicity, PK at LPN-101 compared to placebo in adult subjects with chronic, moderate to severe active SLE. At least 130 subjects will be randomized in a 1:1 ratio to receive a weight-based dose of 3 mg/kg ALPN-101 administered by intravenous infusion via an infusion pump or matching placebo every other week (Q2W) for a total of 12 doses. An overview of the study design is provided in Appendix 15.1.

Randomization will be stratified based by SLE treatment at baseline and geographic region (Appendix 15.5). Subjects will be followed for 4 weeks after the End of Treatment (EOT) visit, 6 weeks after the last dose of study drug. Assessments of adverse events (AEs) and disease activity, and collection of blood and urine for safety laboratory values, biomarkers of disease activity, PK, ADA, and will be performed throughout the study. The Schedule of Assessments is provided in Appendix 15.2.

Each subject will participate for up to 34 weeks, including:

- Screening Period: Up to 42 days prior to first dose date. All subjects must complete all screening assessments and make them available to the team for verification of disease activity. Subjects who appear to meet eligibility criteria must undergo central review and verification of SLE disease activity prior to randomization.
- Treatment Period: Up to 24 weeks from first dose date. Subjects will receive 12 doses of study treatments Q2W. Safety, biologic activity, PK, ADA, will be conducted according to the Schedule of Assessments (Appendix 15.2).
- Follow-up Period: 4 weeks after EOT.

Dense PK will be collected in subjects who agree to participate. Additional PK samples will be collected from these subjects 4 hours following administration of the first dose of study drug, and on days 1, 3 and 7 following the first study drug administration.

Medications that are used for treatment of SLE at baseline should be maintained at stable doses through the Day 169 assessments, except for incidences of toxicity or for a protocol-defined short-term increase (burst and taper) of corticosteroid dose in response to increased disease activity or reduction in corticosteroids (taper) to reduce toxicity in the context of improvement in disease activity.

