Subjects who prematurely discontinue treatment with study drug should have all procedures outlined in the EOT visit and an unscheduled ECG performed as soon as possible, and not later than the next scheduled visit. To minimize missing data for efficacy and safety assessments, subjects who prematurely discontinue treatment, and who do not withdraw from the study, should otherwise continue their regular study visit schedule without receiving study drug. In subjects who are unable to continue their regularly scheduled visits, a follow-up phone call should occur approximately 8 weeks (corresponding to 5X half-life) after the last dose of study drug to determine the status of any ongoing AEs/ SAEs or the occurrence of any new AEs/SAEs.

Subjects who withdraw from the study prematurely (i.e., prior to Day 197), the End of Study (EOS) evaluations should be completed, if possible, preferably within 2 weeks of study drug discontinuation. In addition, a follow-up phone call should occur approximately 8 weeks (corresponding to 5x half-life) after the last dose of study drug to determine the status of any ongoing AEs/SAEs or the occurrence of any new AEs/SAEs.

It should be noted that while N=130 subjects were expected to be randomized in this study, enrollment was stopped at N=76 subjects.

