7.3. Treatment Exposure and Compliance

The extent of exposure to study drug will be summarized for the safety population by treatment group. Exposure duration in days will be calculated as defined in Section 6.2. Descriptive summaries of exposure days and the number and percentage of subjects in each exposure duration category, defined as ≥ 4 weeks, ≥ 12 weeks and ≥ 24 weeks will be presented.

To assess compliance with protocol-specified administration of study treatment, subjects in the safety population who missed a study drug infusion at any scheduled dosing visit prior to treatment completion or discontinuation or who do not receive the targeted amount of study drug are considered non-compliant. The number and percentage of non-compliant subjects will be summarized by treatment group and visit.

Overall compliance will be summarized descriptively. A by-subject listing of study drug administration will be provided.

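### SAP 6.3 divides doses received by elapsed weeks/2, so an early stopper's compliance depends on when end of treatment is dated and can exceed 100% with no dose missed

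*SAP*

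**What the plan says.** SAP 6.3 gives each subject a compliance percentage: "100 x (number of doses received)/(weeks of study participation prior to the end of treatment/2"). It adds no cap and does not define the date on which treatment ends.

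The dosing plan is in Protocol 7.2: "The planned dosing regimen for this study is 3 mg/kg ALPN-101 or placebo IV administered Q2W for 12 total doses". Table 1 places the infusions on Days 1, 15, ..., 155. SAP 4.1 has "Treatment Period: Up to 24 weeks from first dose date", and for completers the EOT visit is Day 169 (Protocol 6.4.12).

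For subjects who stop early, Protocol 4.3.2 wants the EOT procedures "performed as soon as possible, and not later than the next scheduled visit". SAP 4.1 repeats this, and Protocol 6.6.1 says "as soon as possible, preferably within 2 weeks".

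SAP 7.3 uses the percentage only for a descriptive summary. The same section has a separate rule that classes as non-compliant any subject "who missed a study drug infusion at any scheduled dosing visit prior to treatment completion or discontinuation", or who did not receive the targeted amount. Those subjects are counted by treatment group and visit, and a by-subject dosing listing is provided.

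**The concern.** Dosing starts on Day 1, so k infusions with none missed cover only 2(k − 1) weeks from first to last. Dividing by elapsed weeks/2 returns 100% only if a further 14 days pass between the last infusion and the end of treatment. A completer on schedule has those 14 days (Day 155 to Day 169). An early stopper is asked to attend sooner, and the formula then credits more infusions than its denominator expects.

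At stake is whether the compliance table can be read. Values well above 100% would appear for subjects who simply stopped. They would raise the mean most in the arm with more, or earlier, stopping, and could cancel out infusions that were really missed. The percentage would partly measure how quickly the EOT visit was held.

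**Working it through.** **Inputs.** Infusions are every 14 days from Day 1, 12 in total (Protocol 7.2, Table 1). EOT is Day 169 for completers (Protocol 6.4.12), with a window of ±3 days (Table 1). Let k be infusions received with none missed, and g the days from the last infusion to the end of treatment.

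**Formula.** Elapsed days are 14(k − 1) + g, so SAP 6.3 gives

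C = 100k / {[14(k − 1) + g] / 14}.

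**Completer, end of treatment taken as the EOT visit.** At Day 169, 168 days = 24 weeks have elapsed, 24/2 = 12, and C = 100 × 12/12 = 100%. This agrees with the planned 12 doses. Across the visit window (165 to 171 elapsed days) C runs from 101.8% to 98.2%. A completer who missed one infusion scores 100 × 11/12 = 91.7%, which is correct.

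**Early stopper, none missed, end of treatment taken as the EOT visit (C in %).**

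| g (days) | 1 dose | 2 doses | 3 doses | 6 doses |
|---|---|---|---|---|
| 3 | 466.7 | 164.7 | 135.5 | 115.1 |
| 7 | 200.0 | 133.3 | 120.0 | 109.1 |
| 10 | 140.0 | 116.7 | 110.5 | 105.0 |
| 14 | 100.0 | 100.0 | 100.0 | 100.0 |
| 17 | 82.4 | 90.3 | 93.3 | 96.6 |

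For example, two doses at g = 7 give 100 × 2/(21/14) = 133.3%. The right answer in every cell is 100%.

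**End of treatment taken as the last dose (g = 0).** A full completer scores 100 × 12/(154/14) = 109.1%, or 100 × 12/(155/14) = 108.4% if one day is added as SAP 6.2 does for exposure. A one-dose subject gives division by zero, or 1400% with the added day.

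**Offset within a subject.** Take a subject who received 3 of 4 scheduled infusions, including the fourth. The true value is 75.0%. The formula gives 100 × 3/[(42 + g)/14]: 100% at g = 0, 85.7% at g = 7 and 75.0% at g = 14.

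**Offset in an arm mean.** SAP 4.1 gives 76 subjects enrolled; I assume an even split, 38 per arm. One value of 200% in place of 100% adds (200 − 100)/38 = 2.6 points. One of 467% adds (467 − 100)/38 = 9.7 points.

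A mixed illustration, also assumed, has 4 early stoppers after 2, 3, 4 and 6 doses, 6 completers who each miss one infusion, and 28 full completers. The true mean is (4 × 100 + 28 × 100 + 6 × 91.7)/38 = 98.7%. With g = 7 for the stoppers it becomes (133.3 + 120.0 + 114.3 + 109.1 + 2800 + 550)/38 = 100.7%. The minimum is 91.7% either way.

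**The case against.** The strongest reply is that little depends on this number, and that missed infusions are reported elsewhere. SAP 7.3 flags every subject with a missed infusion or off-target amount, counts them by group and visit, and lists dosing by subject. Protocol 10.5.3 also compares the amount given with the amount expected. SAP 7 requires the median, minimum and maximum, so an extreme value would be seen. A reader might infer that the formula hides missed infusions from the study report; these provisions show that it does not. The offset is confined to the overall percentage.

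A reader might also infer that every early stopper scores above 100% by construction. That does not follow. An EOT visit held at the next dosing visit, 14 days on, gives exactly 100% for any number of doses, and a later one gives less. Nor is the percentage part of the safety evaluation: compliance is not among the safety endpoints (SAP 3.2) or safety analyses (SAP 7.8), and no analysis population in SAP 5.1 depends on it.

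Finally, the largest figures need a subject who stops after one dose and attends within days. The documents give no early-stopping rate or timing, so how often this happens is unknown.

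All of this limits the size of the problem and stands. It does not make the formula right. SAP 6.3 is the only per-subject compliance percentage that the SAP defines, and it scores subjects with identical adherence differently according to visit timing.

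**Conclusion.** The formula is wrong as written for early stoppers, and an undefined term makes it worse. Read with the EOT visit as the end of treatment, it is right for completers at Day 169. For early stoppers with no missed infusion it is too high when EOT is less than 14 days after the last dose, right at 14 days and too low beyond that. Read with the last dose as the end, it is too high for full completers as well. The requested prompt EOT visit makes values above 100% likely, though not certain.

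The effect on an arm mean is a few points in plausible cases: 2.6 points for one subject at 200%, and 9.7 for one at 467%. Both figures rest on an assumed 38 subjects per arm. Severity is minor, because missed infusions are counted separately and no efficacy or safety endpoint uses the percentage.

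**What to change.** Replace the formula in SAP 6.3 with: overall compliance (%) = 100 × infusions received / infusions scheduled (Days 1, 15, ..., 155) up to treatment completion or the treatment discontinuation date, maximum 12. State that a dosing visit falling on the discontinuation date counts as scheduled only if the infusion was given.

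Every subject with none missed then scores exactly 100%, whatever the EOT timing. One missed of 4, 6 or 12 scheduled gives 75.0%, 83.3% or 91.7%.

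The cost is one line in the SAP and a small programming change. No new data are needed: SAP 7.3 already requires scheduled dosing visits before completion or discontinuation to be identified, and SAP 7.5.1 already uses a treatment discontinuation date. The percentage would then agree with the non-compliance rule in SAP 7.3 on missed infusions.

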6.4. Treatment-Emergent Adverse Events

TEAEs are defined as AEs that start or worsen in severity on or after the administration of the first dose of study drug through the end of study participation or at least 8 weeks after last study drug administration for subjects who discontinue treatment early.

6.5. Systemic Lupus Erythematosus Responder Index

SRI is a binary composite score defined by meeting all the following criteria:

- Reduction from baseline in SLEDAI-2K total score ≥x, where x=4 points for SRI-4, 5 points for SRI-5, 6 points for SRI-6, 7 points for SRI-7 and 8 points for SRI-8
- No new BILAG-2004 disease activity A scores (severe disease) and no more than 1 new activity score B (moderate disease)
- No worsening from baseline in subjects' lupus disease activity. Worsening is defined by an increase ≥10% (i.e., increase of ≥0.30 on a 3-point scale) in PhGA

6.6. British Isles Lupus Assessment Group-based Composite Lupus Assessment

BICLA response is a binary composite score defined by meeting all the following criteria:

- Reduction in all baseline BILAG-2004 A to B, C or D and baseline BILAG-2004 B to C or D, and no BILAG-2004 worsening in other organ systems, as defined by ≥1 new BILAG-2004 A or ≥2 new BILAG-2004 B
- No worsening from baseline in SLEDAI-2K. Worsening is defined as an increase from baseline of >0 points in SLEDAI-2K total score
- No worsening from baseline in subjects' lupus disease activity. Worsening is defined by an increase $\ge 10\%$ in PhGA (i.e., increase of ≥ 0.30 on a 3-point scale)

Subjects with no BILAG-2004 A or B scores at baseline and no worsening in any organ systems (defined by ≥ 1 new BILAG-2004 A or ≥ 2 new BILAG-2004 B), as well as subjects with a baseline PhGA score ≥ 2.7 on a 3-point scale will be considered as having met the criteria defined above for BILAG and PhGA, respectively.

6.7. Time-to-First Response

Time-to-first response of a specified efficacy endpoint, such as SRI-4 or BICLA, is defined as the number of days from the administration of the first dose of study drug to the date of the visit during which the first response of the specified endpoint is recorded. Time-to-first response is calculated as:

Date of first response – Date of first dose of study drug + 1

Subjects who do not achieve a response will be censored at their EOT date.

6.8. Systemic Lupus Erythematosus Flare

Three definitions will be used to examine the occurrence of SLE flares during the study.

BILAG Flare Index: BILAG-2004 responses will be used to identify SLE flares according to the following severity levels [Gordon, 2003].

- Mild BILAG Flare: One new BILAG-2004 B grade in an organ system with grade C,
 D or E at the previous visit, or 3 or more new BILAG-2004 C grades in organ systems with grade D or E at the previous visit
- Moderate BILAG Flare: Two or more new BILAG-2004 B item in organ systems with grades of C, D or E at the previous visit
- Severe BILAG Flare: One or more new BILAG-2004 A item compared to the previous visit

6.9. Time-to-First Systemic Lupus Erythematosus Flare

Time-to-first SLE flare is defined as the number of days from the administration of first dose to the first occurrence of flare. That is:

Date of first occurrence of SLE flare – date of first dose of study drug + 1

Subjects who do not experience any SLE flares will be censored at their EOT date.

Time-to-first SLE flare will be summarized for each definition of SLE flare.

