7.4.2. Handling of Missing Data and Intercurrent Events (IE)

Intercurrent events in this study include the following:

- IE1: Premature discontinuation of study treatment
- IE2: Restricted/rescue medication use (criteria for restricted/rescue medication use is provided in Section 6.21)

The strategies to be used in the handling of intercurrent events and missing data for efficacy endpoints, when applicable, are provided below:

- Binary endpoints (primary and secondary efficacy endpoints):
 - IE1 and IE2: subject is considered a non-responder (composite strategy)
 - Missing data for Day 169: subject is considered a non-responder
- Continuous endpoints measured through time (SLEDAI-2K total score):
 - IE1 and IE2: data after IE1 and IE2 occurs will not be included in the analysis (hypothetical strategy)
 - Missing data caused by applying the intercurrent event handling described above and other missing data will be handled by the mixed effects models for repeated measures (MMRM) analysis
- Other efficacy endpoints:
 - Treatment policy strategy will be applied and all observed data during the treatment period will be used regardless of IE1 or IE2
 - Missing data for Day 169 for binary endpoints: subject is considered a non-responder for applicable endpoints

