7.6.3. Analysis of Time-to-Event Endpoints

Time-to-event analyses, such as time-to-first SLE flare and time-to-first BICLA response, will be analyzed using a Cox proportional hazards models adjusted for stratification factors (concomitant oral immunosuppressive therapy use at enrollment and geographic region). Subjects who do not experience the specified event will be censored on the date at which the last non-missing response data were collected. For example, in the time-to-first SLE flare, subjects who do not experience flares will be censored on the date of the last available BILAG value. In the analysis of time to first BICLA response, subjects who do not achieve a positive BICLA response will be censored on the date of their last non-missing BICLA response value. Estimated hazard ratios and corresponding 95% CI will be reported. If estimable, median, 25th and 75th percentiles of the time to specified event and corresponding 95% CI will be reported. Time to event secondary efficacy endpoints will be displayed in Kaplan-Meier curves.

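### SAP 6.7 and 6.9 censor event-free subjects at an undefined EOT date, SAP 7.6.3 censors them at their last assessment, and the 28-day cut-off in SAP 7.6 conflicts with the treatment-policy estimand for time-to-first flare

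*SAP*

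**What the plan says.** Three end points apply to the same subjects.

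- **EOT date.** SAP 6.9, on flare: "Subjects who do not experience any SLE flares will be censored at their EOT date". SAP 6.7, on response: "Subjects who do not achieve a response will be censored at their EOT date".
- **Last assessment.** SAP 7.6.3 gives a general rule: "Subjects who do not experience the specified event will be censored on the date at which the last non-missing response data were collected". Its two examples are that "subjects who do not experience flares will be censored on the date of the last available BILAG value" and that "subjects who do not achieve a positive BICLA response will be censored on the date of their last non-missing BICLA response value".
- **28-day cut-off.** SAP 7.6, the parent section of 7.6.3, ends secondary efficacy data at Day 169 for completers. For early stoppers it ends them at the last assessment no more than 28 days after stopping.

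For endpoints outside its binary and SLEDAI-2K groups, SAP 7.4.2 says: "Treatment policy strategy will be applied and all observed data during the treatment period will be used regardless of IE1 or IE2". SAP Table 2 lists time-to-first flare under that strategy, with a hazard ratio as its summary. SAP 6.10 ends exposure for the companion flare-rate endpoint at the last BILAG assessment.

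Protocol 4.3.2 says that early stoppers "should have all procedures outlined in the EoT visit, as well as an unscheduled ECG, performed as soon as possible", no later than the next scheduled visit. Protocol 6.6.1 prefers this within 2 weeks. Subjects who do not withdraw consent then follow the normal visit schedule off drug, which includes BILAG. SAP section 12 also attaches the EOT label to the Day 169 visit. No passage says which date is the EOT date for someone who stopped early.

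**The concern.** Two programmers following different sections of the SAP would build different datasets for the same endpoint, and the protocol cannot settle it: it gives no censoring rule and defers to the SAP.

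One combination is also unsound. Suppose the EOT date is the early EOT visit and flares through Day 169 count, as Table 2 implies. Follow-up after that visit then enters the analysis only if it contains a flare. Whether a subject is censored early depends on what happens later, which the Cox model and the Kaplan-Meier curve assume does not occur. The arm with more early stopping would look worse on flare than it is.

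**Working it through.** **No plan figure to reproduce.** The SAP gives no flare rate, stopping rate, event count or hazard ratio for this endpoint. Its power figures for 65 per arm (82% for SRI-4, 87% for BICLA) reproduce at 82.2% and 86.9%, but they do not depend on censoring.

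**One subject under each reading.** A subject stops drug at Day 57 and stays in the study. The EOT visit is at Day 57 if immediate, or Day 71 if 14 days later (also the next scheduled visit). Post-baseline BILAG visits through EOT are Days 29, 57, 85, 113, 141 and 169.

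| Reading | Never flares: censored at | First flare found at Day 141 |
|---|---|---|
| 6.9, EOT = early visit, Table 2 governs | Day 57 to 71 | Event at Day 141 |
| 6.9, EOT = Day 169 visit, Table 2 governs | Day 169 | Event at Day 141 |
| 7.6.3, Table 2 governs | Day 169 | Event at Day 141 |
| 7.6.3, 28-day cut-off governs | Day 57 + 28 = Day 85 | Not an event |

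Against 7.6.3, the first row drops 169 − 57 = 112 or 169 − 71 = 98 flare-free days if Table 2 governs. If the cut-off governs, the early EOT rule drops 85 − 57 = 28 or 85 − 71 = 14 days. A completer with a Day 169 BILAG and data ending there has the same date under every reading.

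**Direction.** The flare rate is events divided by person-time. Under the first row the numerator keeps events after the EOT visit, while the denominator loses the later time of those who stay flare-free. The rate can only rise, and it rises more with more early stopping.

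**Size, by simulation.** All inputs except the BILAG days are assumptions:

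- true hazard ratio of 1 and a constant flare hazard λ = −ln(1 − p)/169, with p = 30%, 50% or 70% flaring by Day 169
- stopping spread evenly over Days 15 to 141, with the EOT visit 14 days later and every stopper remaining in the study
- 20,000 subjects per arm, Cox model with Efron ties

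| Flaring by Day 169 | Stopping, placebo / ALPN-101 | Table 2 governs: HR by EOT rule / last BILAG | 28-day cut-off: HR by EOT rule / last BILAG |
|---|---|---|---|
| 30% | 10% / 30% | 1.109 / 1.006 | 1.016 / 0.997 |
| 50% | 10% / 30% | 1.069 / 0.988 | 1.021 / 1.003 |
| 70% | 10% / 30% | 1.045 / 0.989 | 1.029 / 1.012 |
| 30% | 20% / 20% | 0.997 / 0.996 | 0.994 / 0.994 |
| 50% | 20% / 20% | 0.988 / 0.988 | 0.985 / 0.985 |
| 70% | 20% / 20% | 1.001 / 0.999 | 0.987 / 0.988 |

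Each single hazard ratio carries simulation error. At 30% flaring there are about 6,000 events per arm, so the standard error of log HR is about √(1/6000 + 1/6000) = 0.018. The two rules share the same simulated subjects, so their ratio is the steadier measure:

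- Table 2 governs: 1.109/1.006 = 1.10, 1.069/0.988 = 1.08, 1.045/0.989 = 1.06
- 28-day cut-off: 1.016/0.997, 1.021/1.003 and 1.029/1.012, each 1.02

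At 50% flaring and 30% stopping, the ALPN-101 flare rate goes from 1.41 to 1.55 per year under Table 2 (1.55/1.41 = 1.10), and from 1.41 to 1.43 with the cut-off. With 20% stopping in both arms the hazard ratio is unaffected, although each arm's own rate still rises (1.41 to 1.50 in the same setting, Table 2 governing).

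A separate simulation with hazards of 1 and 2 per year and stopping over Days 29 to 141 gave a hazard ratio of 1.09 for 30% versus 10% stopping.

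**At the enrolled size.** With 76/2 = 38 per arm, 50% flaring and 10% versus 30% stopping, 1,500 runs gave a type I error of 5.5% (EOT rule) and 4.5% (last BILAG) if Table 2 governs, and 4.1% and 4.0% with the cut-off. There is no clear difference.

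**The case against.** The strongest reply is that SAP 7.6 governs its own subsection. Its 28-day limit would remove the Day 141 flare in the example and shrink the gap to at most 28 days. This stands as a possible reading, and it cuts the effect to about 2%. It does not resolve the matter: the limit contradicts the treatment-policy strategy that SAP 7.4.2 and Table 2 assign to this endpoint, and the two censoring rules still differ.

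A second reply is that the EOT date may simply mean the Day 169 visit. If so, the asymmetry disappears. The text does not say so, and the documents also use EOT for the visit made soon after early stopping.

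Third, 7.6.3, Table 2 and 6.10 all point to the last BILAG, so a careful programmer would probably choose it. That is likely, but 6.9 is the section that defines the endpoint. The weight is limited in any case: this is one secondary endpoint, without multiplicity adjustment, in a trial whose primary objective is safety.

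Three stronger inferences are tempting and should not be drawn:

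- *Completers could be censored at Day 197.* Only 7.6.3 read alone allows this. SAP 7.6 ends their data at Day 169.
- *Time to response is biased in the same way.* The SAP does not say that responses after stopping count as events for it, and stopping makes a subject a non-responder for the binary SRI-4 and BICLA endpoints. It is also not among the listed secondary endpoints.
- *The flare hazard ratio will be off by about 9%.* That needs Table 2 to govern, the early-visit meaning of EOT, unequal stopping and full retention of stoppers. A subject who stops and leaves has nearly the same EOT and last-BILAG date.

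**Conclusion.** The contradiction is certain: 6.7 and 6.9 give one censoring date, 7.6.3 gives another, the EOT date is undefined for early stoppers, and the 28-day limit in 7.6 conflicts with the estimand for time-to-first flare. As written, the hazard ratio for that endpoint depends on which passage is programmed.

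The bias is conditional. It arises in full only if the EOT date is the early EOT visit and Table 2 governs. With 30% versus 10% stopping and stoppers remaining in the study, the null hazard ratio is then about 1.05 to 1.11, against 0.99 to 1.01 with last-BILAG censoring. With the 28-day cut-off it is about 1.02 to 1.03. The hazard ratio is not distorted if stopping is equal between arms or if EOT means Day 169. The stopping and flaring rates are assumptions, since the documents give none. No effect on type I error is shown at 38 per arm, and for time to response only the inconsistency is established. This should be corrected, as a matter of a reproducible and unbiased estimate for a secondary endpoint.

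**What to change.** Delete the EOT-date censoring sentences in SAP 6.7 and 6.9 and keep one rule.

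- **Time-to-first flare:** count events and censor over the same interval. Censor at the last non-missing BILAG on or before the Day 169 analysis visit, whether or not drug was stopped. State in SAP 7.6 that the 28-day cut-off does not apply to this treatment-policy endpoint; without that sentence the SAP still contradicts Table 2.
- **Time to response:** censor at the last non-missing response assessment, as in 7.6.3, no later than Day 169, and use the same cut-off for events and censoring.
- **EOT date:** define it for early stoppers wherever the term remains in the SAP.

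The cost is SAP wording only, because the visits and BILAG data are already collected. The change should be made before unblinding.
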